4.2.3.5 Supplementary Analyses of the Key Secondary Endpoint

Supplementary analyses targeting the impact of intercurrent events: PEOT and/or RM are performed following the strategy discussed in Section 4.2.1.7.2, 4.2.1.7.4 and 4.2.1.7.5.

Another supplementary analysis to examine the impact of different discontinuation rates based on tipping point analysis is performed following the strategy discussed in Section 4.2.1.7.3 by replacing BICLA response by maintained OCS reduction, if the nominal p-value is ≤ 0.05 for primary analysis of maintained OCS reduction.

For subjects with baseline OCS ≥ 10 mg/day prednisone or equivalent, a shift table of reaching a maintained OCS reduction at Week 52 (as defined in Section 4.2.3.1) versus achieving BICLA response at Week 52 (as defined in Section 4.2.1.1) will be provided.

4.2.3.6 Subgroup Analyses

The subgroup analyses will be performed for the following stratification factors excluding the subgroup OCS dose at baseline (< 10 mg/day versus ≥ 10 mg/day prednisone or equivalent), i.e.

- Region (mainland China versus not mainland China)
- SLEDAI-2K score at screening (< 10 points versus ≥ 10 points).

The analysis methods are the same as described above for the maintained OCS reduction endpoint in Section 4.2.3.4.

4.2.4 Key Secondary Endpoint - Flares

4.2.4.1 Definition

The key secondary endpoint used to evaluate the effect of anifrolumab versus placebo on flares is the difference in annualized flare rate through Week 52.

A flare is defined as either 1 or more new BILAG-2004 A or 2 or more new BILAG-2004 B items compared to the previous visit (i.e., a worsening from an E, D, or C score to a B score in at least 2 organ systems or a worsening from an E, D, C, or B score to an A score in any one organ system compared to the previous visit).

4.2.4.2 Derivations

The occurrence of a new flare will be checked for each available visit versus the previously available visit up to Week 52. If no flare occurred, the number of flares will be set to 0. Otherwise, all flares will be counted leading to a maximum number of flares of 13.

The annualized flare rate is calculated as the number of flares divided by the flare exposure time in days multiplied with 365.25. The flare exposure time is the time up to the date of last available BILAG-2004 assessment up to and including Week 52 during the double-blind treatment period. It is derived as the date of last BILAG-2004 assessment minus date of first administration of IP + 1.

For the supplementary analyses of flares while on treatment, the flare exposure time is the time up to the date of last dose of IP + 28 days. It is derived as date of last dose of IP + 28 days - date of first dose of IP + 1. All flares occurring within the double-blind treatment period and the flare exposure time are considered for this analysis.

4.2.4.3 Handling of Dropouts and Missing Data

Participants who prematurely discontinue from treatment are analyzed according to the date of last available BILAG-2004 assessment up to and including Week 52, except for Section 4.2.4.6 on-treatment analysis. Missing post-baseline BILAG-2004 assessments are imputed using LOCF. This applies only once. Missing post-baseline assessments after LOCF are counted as no flare in annualized flare rate analysis.

4.2.4.4 Primary Analysis of Key Secondary Endpoint – Flares

The flare rate in the anifrolumab treatment group is compared to the flare rate in the placebo group using a negative binomial regression model. The response variable in the model is the number of flares over the 52-week treatment period. The model includes covariates of treatment group, and the stratification factors. The logarithm (to base e) of the follow-up time (flare exposure time as defined in Section 4.2.4.2) is used as an offset variable in the model to adjust for participants having different exposure times. If there are less than 10 flare events in total for a subgroup based on stratification factor or less than 2 events in either treatment group for that subgroup, then the corresponding stratification factor will be removed in the model. The estimated treatment effect and the corresponding 95% CI, as well as the 2-sided nominal p-value are presented.

4.2.4.5 Sensitivity Analysis of Key Secondary Endpoint – tipping point analysis

Firstly, a missing at random (MAR) analysis will be performed where for each participant the rate after withdrawal λ_1 is assumed to be the same as their rate before withdrawal λ_2 , which itself is calculated based on their randomized treatment group and baseline covariates included in the negative binomial regression model as section 4.2.4.4.

A tipping point analysis will then be performed if the p-value for the primary analysis is ≤ 0.05 , where the rate after withdrawal will be modified to $\delta\lambda_2$. A series of analyses will be performed with a range of increasing deltas for the two arms (δ_P and δ_A for placebo and anifrolumab 300 mg groups, respectively) so that one could assess at which point the study conclusions would change from favorable to unfavorable, i.e., to identify a tipping point.

In this assessment, the placebo group is assumed to improve after withdrawal and the anifrolumab group is assumed to worsen after withdrawal. Therefore, $\log(\delta_P)$ will be varied from -1.5 to 0 in increments of 0.5 and $\log(\delta_A)$ will be varied from 0 to 1.5 in increments of 0.5. This corresponds to deltas between 0.22 and 1 for the placebo group and deltas between 1 and 4.5 for the anifrolumab 300 mg group. If statistical significance is maintained among the matrix of possible δ combinations, the comparison is deemed robust to missing data. For a given comparison, if a tipping point is observed with analysis at 0.5 increments, the δ values will be further refined down to 0.25 increments for the relevant interval. For example, if a tipping point is identified when increasing $\log(\delta_A)$ from 1 to 1.5, the matrix will be expanded to include also the value $\log(\delta_A) = 1.25$. The values for δ (and the corresponding increments) will be checked during the dry run and adapted as necessary.

4.2.4.6 Supplementary Analysis of the Key Secondary Endpoint - Flares while on treatment – targeting the impact of PEOT

The flare rate in the anifrolumab treatment group will be compared to the flare rate in the placebo group using a negative binomial regression model as section 4.2.4.4. The response variable in the model is the number of flares while on treatment (i.e., up to last administration of IP + 28 days during the double-blind treatment period). The model includes covariates of treatment group, and the stratification factors. The logarithm (to base e) of the follow-up time (flare exposure time as defined in Section 4.2.4.2) is used as an offset variable in the model to adjust for participants having different exposure times. The estimated treatment effect and the corresponding 95% CI are presented.

A summary of the annualized flare rate by descriptive statistics as well as a summary of the number and percentage of participants with no flares, at least one flare, 1 flare, 2 flares, and 3 or more flares, respectively, are presented by treatment group.

4.2.4.7 Supportive Analysis of the Key Secondary Endpoint

Time to first flare is assessed for flares as defined in Section 4.2.4.1. The time to first flare is derived as date of first flare minus date of first administration of IP. If the participant did not have a flare, the time to flare is censored at the end of the flare exposure time (as defined in Section 4.2.4.2).

Cox proportional hazards models, as reported in Section 4.2.1.7.7, (using a profile likelihood approach with ties=Efron) including the covariates of treatment and the

stratification factors are used to estimate the treatment effect. The estimated HRs and corresponding 95% CIs are presented for the effect of the treatment group.

Time to first flare distribution is compared between anifrolumab and placebo using a stratified log-rank test adjusting for the same randomization stratification factors used in the stratified Cox model.

4.2.4.8 Subgroup Analyses

The subgroup analyses will be performed for the following stratification factors, i.e.

- Region (mainland China versus not mainland China)
- SLEDAI-2K score at screening (<10 points versus ≥ 10 points)
- OCS dose at baseline (<10 mg/day versus ≥ 10 mg/day prednisone or equivalent).

The analysis methods are the same as described above for the flare rate endpoint in Section 4.2.4.4.

4.2.5 Other Secondary Endpoint - Skin Lesions

4.2.5.1 Definition

The secondary endpoint used to evaluate the effect of anifrolumab versus placebo on inflammatory cutaneous lupus lesions in participants with baseline CLASI activity score ≥ 10 is the difference in the proportion of participants with $\geq 50\%$ reduction in CLASI activity score at Week 12. An at least 50% reduction in CLASI activity score is defined as meeting all of the following criteria:

- Achieve $\geq 50\%$ reduction of CLASI activity score at Week 12 compared to baseline.

4.2.5.2 Derivations

The CLASI activity score is defined in Section 4.1.6.1. A $\geq 50\%$ reduction is reached if the percentage change is $\leq -50\%$.

4.2.5.3 Handling of Dropouts and Missing Data

If any of the criteria cannot be evaluated at any visit up to Week 12 (e.g., due to missing values), the data for that criterion will be imputed using LOCF and at least 50% reduction in CLASI activity score derived based on the complete data. This applies only once. Missing data after the imputed LOCF value will be imputed as non-responder. For example, if any of the Week 12 criteria data is missing and Week 8 data is not missing, the missing Week 12 criteria data will be imputed using the corresponding Week 8 data. Otherwise, the participant will be defined as not reaching a $\geq 50\%$ reduction in CLASI activity score at Week 12.

LOCF records are not used in the repeated measures models.

4.2.5.4 Primary Analysis of the Secondary Endpoint – Skin Lesions

The analysis includes only subjects with baseline CLASI activity score ≥ 10 .

The same CMH approach as described in Section 4.2.1.5 for the primary endpoint will be used to estimate the treatment difference between anifrolumab and placebo in subjects with baseline CLASI activity score ≥ 10 . Longitudinal presentations of the results over time (i.e., for each post-baseline visit up to Week 52 during double blind treatment period) based on this analysis will be created.

4.2.5.5 Supplementary Analysis of the Secondary Endpoint – targeting the impact of burst and taper

A supplementary analysis is provided if at least 10 participants in a treatment arm have a burst and taper of OCS or IM (intramuscular) steroids during the first 12 weeks of treatment. The CMH analysis will be repeated for the at least 50% reduction in CLASI activity score (including all criteria) at Week 12 excluding subjects administered a burst and taper of OCS or IM steroids during the first 12 weeks of treatment. A burst and taper of OCS or IM steroids is defined as an OCS increase above the daily dose at Day 1 or any IM steroid dose.

4.2.5.6 Supportive Analysis of the Secondary Endpoint- change from baseline in CLASI activity and damage score

Change from baseline in CLASI activity score and CLASI damage score, respectively, are analyzed using the repeated measures models with fixed effects for baseline value, treatment group, visit, treatment*visit interaction and stratification factors, and participant as random effect. Covariance parameters will be estimated using restricted Maximum Likelihood method and Kenward Rogers denominator degrees of freedom will be used for the tests of fixed effects. An unstructured covariance matrix will be used. In case of convergence issues, the following alternative structures are used for fitting (in that order): Heterogeneous Toeplitz, heterogeneous AR(1) (1st order autoregressive), Heterogeneous CS (compound symmetry), Homogeneous CS. Results will be presented in terms of the adjusted means for each treatment group, estimates of treatment differences, and associated 2-sided CIs for each visit up to Week 52 during double blind treatment period.

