**Table 7 Permitted medications for SOC SLE**

Permitted SOC SLE	Limitations of Use
OCS	
 
Oral prednisone or equivalent up to <math>\leq 40</math> mg/day is permitted from at least 2 weeks prior to signing of the informed consent. The dose of oral prednisone must remain stable at least 2 weeks prior to Randomisation.
 
Where prednisone is the single SOC medication [i.e., the participant is not concurrently receiving any medications listed in Section 3.1 #7], a dose of oral prednisone <math>\geq 7.5</math> mg/day but <math>\leq 40</math> mg/day (or prednisone equivalent) for a minimum of 8 weeks prior to Randomisation is required.
 

Intramuscular corticosteroids	
 
Participants with increased SLE disease activity may receive 1 intramuscular injection of corticosteroids (methylprednisolone <math>\leq 80</math> mg or equivalent) instead of a burst and taper of OCS described above between Day 1 and Week 12.
 
May only be administered after all assessments and investigational medicinal product infusion have been completed at the visit.
 

Corticosteroid bursts and tapers	
 
Participants with increased SLE disease activity may receive 1 permitted burst and taper of corticosteroids between Day 1 and Week 12. Additional details on burst and taper for SLE and non-SLE (e.g., asthma or COPD exacerbation) disease activity are provided in Sections 7.7.1.4 to 7.7.3.
 

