- If a subject has OCS or equivalent total daily dose above their Day 1 dose for a period >14 days, ending before or on Week 12, the subject will be considered to have an ICE of RM use from the start date of the rule break until 12 weeks after the end date of the burst i.e. until the end date of the burst + 84 days.

12 weeks takes into consideration the biologic half-life of the treatment (18-36 hours) and the clinical effect of the increased steroids.

These intermittent ICEs of RM use will be documented and captured in the clinical database.

For non-SLE steroid use, details are provided in the 7.4, rule # RM 20.1-20.3. As stated in the CSP, Section 7.7.2, the participants are allowed during the DB treatment period to receive one additional course of burst and taper corticosteroids for increased non-SLE disease activity between Week 12 and Week 40. To not restrict the manual review, the time point of when a potential burst occurred and the number of bursts has not been implemented in the programming rule. This to ensure that all concomitant therapy for this reason are reviewed manually by the MRT.

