Supplementary Analysis of the Secondary Endpoint – targeting the impact of burst and taper.	$\geq 50\%$ reduction in CLASI score	Asian adults with moderate-to-severe SLE with baseline CLASI activity score ≥ 10 , excluding subjects administered a burst and taper of OCS or Intramuscular (IM)	Composite strategy where RM/PEOT/Death=NR	Difference in proportions between interventions (CMH), Week 12	4.2.5.5

Statistical category	Endpoint	Population	Intercurrent event strategy	Population level summary (analysis)	Details in section
		steroids during the first 12 weeks of treatment			
Supportive Analysis of the Secondary Endpoint - change from baseline in CLASI activity and damage score	Change from baseline in CLASI activity and damage score.	Asian adults with moderate-to-severe SLE	Treatment policy where PRM/PEOT/Death=ignored	Difference in mean change from baseline between interventions (repeated measures model), over time up to Week 52	4.2.5.6
Objective 6: To assess the difference between anifrolumab and placebo on the proportions of participants with reduction in the number of swollen and tender joints at Week 52 in the sub-group of those with ≥ 6 swollen and ≥ 6 tender joints at baseline					
Primary Analysis of the Secondary Endpoint – joint count	50% improvement in joint counts at Week 52	Asian adults with moderate-to-severe SLE with ≥ 6 swollen and ≥ 6 tender joints at baseline	Composite strategy where RM/PEOT/Death=NR	Difference in proportions between interventions (CMH)	4.2.6.4
Supportive Analysis of the Secondary Endpoint – Change from baseline in the number of joints	Change from baseline in number of swollen, tender and active joints	Asian adults with moderate-to-severe SLE	Treatment policy where PRM/PEOT/Death=ignored	Difference in mean change from baseline between interventions (repeated measures model), over time up to Week 52	4.2.6.5
Supportive analysis of the Secondary Endpoint – joint count	20% improvement in joint counts at Week 52	Asian adults with moderate-to-severe SLE	Composite strategy where RM/PEOT/Death=NR	Difference in proportions between interventions (CMH)	4.2.6.6

Statistical category	Endpoint	Population	Intercurrent event strategy	Population level summary (analysis)	Details in section
		with ≥ 6 swollen and ≥ 6 tender joints at baseline			

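### The supplementary analysis of steroid bursts for Week 12 CLASI excludes participants on a post-randomisation event, so the difference it reports can be biased (minor)

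*SAP*

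**What the plan says.** The main analysis of the skin endpoint (SAP 4.2.5.4) takes all participants with baseline CLASI activity of at least 10. It compares the proportions with at least a 50% reduction at Week 12 by stratified CMH, with restricted medication (RM), premature end of treatment (PEOT) and death counted as non-response.

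SAP 4.2.5.5 adds one supplementary analysis of the same binary endpoint. It repeats the CMH analysis "excluding subjects administered a burst and taper of OCS or IM steroids during the first 12 weeks of treatment". A burst is "defined as an OCS increase above the daily dose at Day 1 or any IM steroid dose", with no limit on duration or reason. The analysis is conditional: "A supplementary analysis is provided if at least 10 participants in a treatment arm have a burst and taper". The matching row of SAP Table 2 (Objective 5) puts the exclusion in the population column, and its strategy column reads "Composite strategy where RM/PEOT/Death=NR".

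On who gets a burst, Protocol Table 7 says: "Participants with increased SLE disease activity may receive 1 permitted burst and taper of corticosteroids between Day 1 and Week 12". Protocol 7.7.3.1 also allows the burst for non-SLE causes. SAP 4.1.8.1 treats a burst as RM only when a rule is broken, for example by a second burst or by more than 14 days above the Day 1 dose. RM status then lasts until 84 days after the burst ends. The reason given is that "12 weeks takes into consideration the biologic half-life of the treatment (18-36 hours) and the clinical effect of the increased steroids".

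**The concern.** A participant with one permitted burst is not an RM case, so the main CLASI analysis uses the observed Week 12 result. That participant may count as a responder with recent extra steroid on board. SAP 4.1.8.1 dismisses confounding by early bursts only for the primary endpoint at Week 52. At Week 12 its own carry-over period points the other way: a burst ending on Day 1 plus 84 days reaches Day 85, which is the scheduled Week 12 day in SAP Table 1. So every burst in the first 12 weeks is still within that period on the scheduled Week 12 day.

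The sensitivity question is therefore a fair one, and SAP 4.2.5.5 is the only binary CLASI analysis that asks it. The weakness is the method. Exclusion keeps only participants who needed no burst, and that need can depend on both prognosis and treatment. If placebo has more bursts, more poor-prognosis participants leave placebo than leave anifrolumab, and randomisation no longer protects the comparison. A reader using this analysis to judge whether steroids explain the skin result could be misled in either direction.

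Protocol 8.5 says the secondary endpoint analyses use all data captured in the treatment period. The BICLA and SRI(4) supplementary analyses of RM and PEOT keep participants in and change how the event is handled. The one BICLA analysis that removes people (SAP 4.2.1.7.6) does so on baseline features.

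**Working it through.** **No figure to reproduce.** The documents state no burst rate, no CLASI response rate and no size for the subgroup with CLASI of at least 10. All rates below are assumptions.

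**Model 1: two prognostic groups, no drug effect on response.** A share q is flare-prone. Response is rS in the others and rF in the flare-prone. Burst probability is 5% in the others; in the flare-prone it is bP on placebo and bA on anifrolumab.

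- True rate in both arms = (1-q)·rS + q·rF.
- Retained in an arm: kS = (1-q)·0.95 and kF = q·(1-b).
- Rate after exclusion = (kS·rS + kF·rF) / (kS + kF).

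First scenario in full (q = 0.30, rS = 0.50, rF = 0.20, bP = 0.60, bA = 0.30):

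- True rate: 0.70·0.50 + 0.30·0.20 = 41.0% in each arm.
- Placebo: kS = 0.665, kF = 0.120; (0.3325 + 0.0240)/0.785 = 45.4%.
- Anifrolumab: kS = 0.665, kF = 0.210; (0.3325 + 0.0420)/0.875 = 42.8%.
- Difference: -2.6 points, where the truth is 0.

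| q | rS / rF | bP / bA | True difference | After exclusion | Burst = non-response |
|---|---|---|---|---|---|
| 0.30 | 0.50 / 0.20 | 0.60 / 0.30 | 0 | -2.6 | +1.8 |
| 0.30 | 0.50 / 0.10 | 0.80 / 0.30 | 0 | -6.3 | +1.5 |
| 0.40 | 0.55 / 0.10 | 0.80 / 0.30 | 0 | -9.3 | +2.0 |
| 0.30 | 0.50 / 0.20 | 0.45 / 0.45 | 0 | 0.0 | 0.0 |

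The last column is the numerator alone, kS·rS + kF·rF, since everyone stays in the denominator. In the first row it is 0.3745 - 0.3565 = +1.8 points.

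With a true effect of +20 points in both groups, the same formula gives:

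- +17.4 points (q = 0.30, placebo response 0.35 / 0.05, bursts 0.60 / 0.30);
- +12.8 points (q = 0.40, placebo response 0.40 / 0.05, bursts 0.80 / 0.30).

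**Model 2: continuous severity, no drug effect on response.** Response is 35% in both arms. A burst goes to the most severe 30% on placebo and 15% on anifrolumab. Severity and non-response are bivariate normal with correlation ρ. The probability of responding without a burst is the bivariate normal probability below both cut-offs; dividing by (1 - burst share) gives the rate after exclusion.

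| ρ | After exclusion | Burst = non-response |
|---|---|---|
| 0 | 0.0 | +5.25 |
| 0.3 | -2.5 | +3.9 |
| 0.5 | -4.4 | +2.8 |
| 0.7 | -6.5 | +1.5 |

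At ρ = 0 the last column is 0.35·(0.85 - 0.70) = +5.25 points.

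The two models agree on two things. Exclusion pulls the difference against the arm with more bursts. Counting a burst as non-response credits the arm with fewer.

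**The case against.** The strongest reply is that this is a labelled supplementary analysis with an openly stated population, while Objective 5 is answered by SAP 4.2.5.4, which has no exclusion. CLASI is an other secondary endpoint with no confirmatory test, and its supplementary analyses were deliberately reduced. The alternative is not neutral either. Burst = non-response shows a benefit where there is no effect on skin response (+1.5 to +5.25 points above), and it scores bursts for non-SLE causes, or for activity in organs other than skin, as skin failure. All of this stands. It limits the severity and shapes the fix, but it does not make the exclusion a valid randomised comparison.

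Four stronger readings are tempting and are not supported:

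- *The exclusion replaces the composite strategy.* Table 2 keeps that strategy for those who remain. A permitted burst was never under it, so exclusion displaces an observed outcome. Only rule-breaking bursts lose a non-responder status by being dropped.
- *The gap from burst = non-response measures the bias.* With 35% against 50% response among those without a burst, exclusion gives 15.0 points. Burst = non-response gives 0.85·50 - 0.70·35 = 18.0 points at burst rates of 30% placebo and 15% anifrolumab, and 0.70·15 = 10.5 points at 30% in both arms. These are two estimands, not a truth and an error.
- *The trigger means the analysis runs only when the exclusion is large.* SAP 4.2.5.5 does not say whether the 10 are counted in the whole arm or in the CLASI subgroup, nor whether one arm or both must reach it. Over a whole arm, 10/130 is 7.7%. Only on an assumed subgroup of 26 to 52 per arm (20 to 40% of 130) is it 38% to 19%.
- *The main CLASI result is compromised.* Nothing in SAP 4.2.5.4 uses the exclusion.

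**Conclusion.** The point holds as a minor one. SAP 4.2.5.5 conditions on an event after randomisation that can reflect disease activity and can differ by arm, so its CMH difference is not protected by randomisation. Under the assumed rates, with no drug effect on skin response and more bursts on placebo, the shift is about -2.5 to -9 points. With equal burst rates and no drug effect it is zero. The direction in this trial cannot be told from the documents: it depends on burst rates they do not give and on how closely bursts track non-response, which non-SLE bursts would weaken.

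**What to change.** In SAP 4.2.5.5 and the matching Table 2 row:

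- Keep every FAS participant with baseline CLASI activity of at least 10.
- Set anyone with a burst, as already defined there, before the Week 12 assessment to non-responder, and run the same CMH analysis.
- Drop the 10-participant trigger for this analysis.
- If the exclusion analysis is still wanted, show it as a descriptive display only. If it keeps the trigger, say which arm or arms and which participants are counted.
- State that burst = non-response is a different estimand: it counts burst avoidance as benefit and scores non-SLE and non-skin bursts as failure. Present it beside the unchanged main CLASI analysis, not in its place.

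The cost is a few lines of SAP text and one response flag, with no new data. Response rates in this analysis will be somewhat lower than in the main one. Protocol 8.1 requires the final SAP amendment before unblinding, so the change belongs before then.
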